16.7 Indemnity

Sponsor recognizes its liability in law to compensate for any injury sustained by a subject participating in this clinical investigation but only to the extent the study has been conducted in compliance with the protocol.

16.8 Insurance

All subjects enrolled in this study are covered by Clinical Trial Liability Insurance. The name and address of the relevant insurance company, the certificate of insurance, the policy number and the sum insured is provided in the Investigator's Site File.

16.9 Investigators Responsibilities

- Sign and adhere to the Clinical Trail Agreement (CTA).
- Sign and adhere to all of the required elements of the Study Protocol.
- Resolve queries in a timely manner.
- Participate in Investigator meetings as required.
- Comply with the 2013 Declaration of Helsinki and the General Data Protection Regulation (GDPR) and Data Protection Act 2018.
- Obtain written Informed Consent from each study participant before any study specific procedures are performed.
- Complete all required case report forms (CRFs) for each subject.
- Comply with all applicable regulations and codes of approvals from Ethics Committees and other regulatory authorities.
- Notify Sponsor/CRO of any personnel changes at site that may affect the study protocol.
- Retain all records and study files until Sponsor/CRO notifies that files may be destroyed.
- Allow direct access to source data/documents, including subject records, in case of monitoring, auditing and/or inspection by the Ethics Committee and other regulatory authorities.

The investigator is responsible for the preparation and submission of the reports listed in table below:

Report	Submitted to	Description
All serious adverse events (SAE's), device deficiencies that may have led to an SAE if a) suitable action had not been taken or b) intervention had not been made or c) if circumstances had been less fortunate and new findings/updates in relation to already reported events.	Sponsor & EC	The investigator's report on any SAEs must be submitted within 3 calendar days after the investigator first learns of the event.
Withdrawal of/EC approval	Sponsor	The investigator must report a withdrawal of reviewing EC approval within 5 working days.
Failure to obtain Informed Consent	Sponsor & EC	Notification must be made within 5 working days of use of the device.
Emergency deviations from the protocol	Sponsor and EC	Notification must be made within 5 working days of the occurrence of an emergency deviation (made to protect the life or physical well-being of a patient). If the deviation affects the rights, safety, or welfare of the patients (and is not an emergency), or the scientific soundness of the investigation, prior approval must be obtained from Stimdia Medical, the reviewing EC. All deviations must be documented on a Protocol Deviation Form
Progress Report	Sponsor & EC	The investigator must submit a progress report on an annual basis or as required by the governing regulatory agencies.
Final Report	Sponsor & EC	This report must be submitted within 3 months after termination or completion of the clinical study.

16.10 Sponsor Responsibilities

Stimdia Medical will maintain all records pertaining to the investigation including:

- EC approvals
- Signed Investigator Agreements and related materials
- Site monitoring reports
- Records concerning adverse device events
- All CRFs and received source documentation
- Financial Disclosure Forms
- Site Monitoring Visit Log
- All correspondence

Stimdia Medical or its approved representative is responsible for the preparation and submission of the reports listed below:

Report	Submitted to	Description

All serious adverse events (SAE's), device deficiencies that may have led to an SAE if
 
a) suitable action had not been taken or
 
b) intervention had not been made or
 
c) if circumstances had been less fortunate
 
and new findings/updates in relation to already reported events.
 
Reportable events occurring in Third Countries in which a clinical investigation is performed under the same clinical investigation plan. This includes events occurring in third Countries after European sites have closed.
	National Competent Authority (NCA)	The sponsor or approved representative report on any SAEs must be submitted within 2 days after the sponsor or approved representative first learns of the event.

Any other reportable events such as:
 
 - any SAE, - any Device Deficiency that might have led to a SAE if: 
a) suitable action had not been taken or
	NCA	Any other reportable events or a new finding/update to it: immediately, but not later than 7 calendar days following the date of awareness by the sponsor of the new reportable event or of new information in relation with an already reported event.

Report	Submitted to	Description
b) intervention had not been made or c) if circumstances had been less fortunate - new findings/updates in relation to already reported events.		
Withdrawal of EC approval	EC, Investigators & approving regulatory agency(s)	Notification, when appropriate, will be made within 5 working days after Stimdia Medical receives notice of withdrawal of EC approval.
Withdrawal of regulatory agency approval (e.g. HPRA, SUKL)	EC & Investigators	Notification will be made within 5 working days after Stimdia Medical receives notice of withdrawal of regulatory agency approval.
Safety Reports	NCA	
The EU requires that safety line listings and a cover letter that contains an assessment of the safety data and whether or not safety measures need to be taken and justification must be submitted quarterly.
 
The EU requires an annual safety report that must include any new findings from the literature and the investigator's brochure must also be updated annually.

Progress Report	EC, Investigators & regulatory agencies	A progress report will be submitted at least yearly or as required by the EC or governing regulatory agencies.
Recall and Device Disposition	EC, Investigators & regulatory agencies	Notification will be made within 30 working days of Stimdia Medical's request that an investigator return, repair or otherwise dispose of any devices. Such notification will state why the request was made.
Notification of Termination or Completion	EC, Investigators & regulatory agencies	Notification will be made within 90 days.
Final Report	EC, Investigators & regulatory agencies	A final report will be submitted within 3 months after study completion or termination and be signed by the investigator.
Failure to Obtain Informed Consent	Regulatory agencies	Notification will be made within 5 working days of receipt of notice.

Report	Submitted to	Description
Emergency Deviations from Investigational Plan	EC	Notification will be made within 5 working days after Stimdia Medical learns of an emergency deviation from the Investigational Plan where the deviation was made to protect the life or physical well-being of a subject.

16.11 Statement of Compliance

- Sponsor and Investigator will conduct the clinical investigation in accordance with the ethical principles that have their origin in the Declaration of Helsinki and General Data Protection Regulation (GDPR) and Data Protection Act 2018.
- Sponsor and Investigator will comply with EN ISO 14155:2011 and any regional or national regulations, as appropriate.
- Investigator will not begin the clinical investigation until Investigator obtains the required written approval or favorable opinion from the EC or regulatory authority, if appropriate.
- Investigator will follow any additional requirements imposed by the EC or regulatory authority, if appropriate.
- Sponsor will provide insurance for subjects.

16.12 Publication Policy

At the conclusion of the trial, a multi-center manuscript will be prepared for publication in a reputable scientific journal by the Sponsor, Stimdia Medical, Inc. The study will be registered in clinicaltrials.gov.

CRF0012	X	X	X	X	X	X	X	X	X	X	X	X
CRF0013	X	X	X	X	X	X	X	X	X	X	X	X
CRF0014	X	X	X	X	X	X	X	X	X	X	X	X
CRF0015	X	X	X	X	X	X	X	X	X	X	X	X
CRF0016	X	X	X	X	X	X	X	X	X	X	X	X
CRF0017	X	X	X	X	X	X	X	X	X	X	X	X

2. ANALYSIS OBJECTIVES

The company informed the FDA of plans to conduct a First in Human feasibility study within an OUS Tier I country (Canada, Europe or Australia) and stated:

As part of this study the following would be evaluated

- a) Confirmation of the stimulation leads are easily deployed under ultrasound guidance
- b) Confirmation that the diaphragm is easily stimulated without collateral stimulation similar to the Taira publication in references.
- c) Confirmation of appropriate candidates for a pivotal study. Trending demonstrating that time to extubation is decreased when compared to historical data in similar patient population.

The first two patients enrolled in the trial will be analyzed specifically for safety of the procedure in terms of nerve damage which could result from electrical stimulation or mechanical damage due to lead insertion, patient movement or lead removal and any other adverse events. Compound motor action potential and nerve conduction time between the neck and diaphragm will be evaluated in the first two pilot patients. Since these patients are stimulated on the left phrenic nerve only, they will be included for the safety analysis only. The enrollment of subsequent patients was contingent upon these patients showing no damage to the phrenic nerve at ~30 days post stimulation in terms of the CMAP study, follow up x-ray and any reported adverse events deemed relevant to the procedure.

Primary and secondary endpoints for the study will be evaluated statistically in terms of per protocol (PP) and intent-to-treat (ITT) analysis. The clinical study protocol CIP0001 defined intent-to-treat as "All patients that were attempted to be treated with the PEPNS System but the procedure was aborted." The

	PEPNS Study Statistical Analysis Plan <small>CONFIDENTIAL: THIS DOCUMENT AND ALL INFORMATION CONTAINED HEREIN IS PROPRIETARY TO STIMDIA MEDICAL, INC. AND IS NOT TO BE DISCLOSED WITHOUT THE EXPRESS WRITTEN PERMISSION OF STIMDIA MEDICAL, INC.</small>	Document Number SAP0001	Rev. Level 1
---	--	-----------------------------------	------------------------

primary analysis will be per protocol and the secondary analysis will be intent-to-treat. Time of weaning from mechanical ventilation and diaphragm thickness from 0 to 48 hours will also be analyzed.

In addition, there may be additional analyses conducted and other tables and graphs created for the final clinical study report based on the outcomes of the initial analyses and additional data points of interest.

An interim analysis may be run and this was allowed in the protocol. See Statistical Methodology section for greater details.

PRIMARY ENDPOINTS

The primary endpoints for the study relate to the ability of the therapy to mobilize the diaphragm and of the PEPNS system to stimulate specific levels of work of breathing.

- Capture of the Left and/or Right Phrenic Nerve > 80% with an output parameter of < 10.5 volts.
- WOB (Work of Breathing) kept between 0.2 Joules/L and 2 Joules/L for 80% of stimulated breaths.

The capture of the left and right phrenic nerve will be demonstrated during setup and by maintaining the WOB between 0.2 and 2 Joules/L. The stimulation voltage resultant from the tissue impedance and the user set current will be logged and evaluated to ensure it is less than 10.5 volts. Capture will also be evaluated in terms of synchrony.

The ability of the stimulation pulse to capture the diaphragm will be assessed using WOB (Work of Breathing Measurements). A logistic regression model with successful capture as the outcome will be used. The model will include repeated measurements within a subject.

Model:

$\text{capture} = (\text{timepoint}) (\text{subject})$

where subject is a random effect, and the outcome of capture is yes/no based on whether the stimulation captures the diaphragm.

Capture for this analysis is defined as synchrony of the stimulated breath with the output parameter < 10.5 volts and WOB between 0.2 and 2.0 Joules/L. Synchrony will be achieved if the lag time between start of inspiration and start of stimulation is less than 88 ms.

Hypothesis:

H_0 : The proportion of capture is less than or equal to the performance goal (PG) of 80%. Note: This hypothesis used a 90% performance goal in the protocol for the purposes of sample size calculation to ensure that there would be sufficient data to achieve the 80% performance goal when taking into account lost to follow up due to death, etc.

$H_0: \hat{p}_1 \leq \text{PG}$

H_A : The proportion of capture is greater than the performance goal of 80%.

$H_A: \hat{p}_1 > \text{PG}$,

where \hat{p}_1 is the estimated proportion of capture from the logistic model accounting for repeated measurements within a subject.

Sample Size:

This sample size calculation reflects the use of a 90% performance goal as noted above in the hypothesis section and in the CIP. Again, this was done to ensure that there would be sufficient data to achieve the 80% performance goal when taking into account lost to follow up due to death, etc. The following

	PEPNS Study Statistical Analysis Plan <small>CONFIDENTIAL: THIS DOCUMENT AND ALL INFORMATION CONTAINED HEREIN IS PROPRIETARY TO STIMDIA MEDICAL, INC. AND IS NOT TO BE DISCLOSED WITHOUT THE EXPRESS WRITTEN PERMISSION OF STIMDIA MEDICAL, INC.</small>	Document Number SAP0001	Rev. Level 1
---	--	-----------------------------------	------------------------

assumptions were the basis for the sample size calculation for the performance endpoint evaluating stimulation capture of the diaphragm:

- Power: 80%
- 1-sided α : 0.025
- Performance goal: 90%
- Expected success rate: 97.5%

With an anticipated success rate of 97.5% and a performance goal of 90%, 80 observations would yield $\geq 80\%$ power. Note that, for the purposes of sample size calculations, the observations are assumed to be independent. However, the primary analyses will account for within patient correlation, as described below. Increasing the number of observations will increase the statistical power.

Methods:

The proportion of successful capture will be analyzed using a logistic regression model accounting for patient as a random effect. The null hypothesis will be tested comparing the lower bound of the 95% two-sided confidence interval for the estimated percent agreement to the performance goal of 80% (see note above). If the lower bound is greater than 80%, the null hypothesis will be rejected and the endpoint will be considered met.

If the logistic regression model does not converge (i.e. it does not provide reliable estimates of diaphragm capture), other methods will be used to characterize the capture rate. The method used will be dependent on the data and will be described in detail along with the reasons for using that method.

An interim analysis of the primary endpoints may be done on the first 10 patients that were stimulated on both phrenic nerves. If they are met the secondary and other remaining analyses will also be performed. If not, the study will continue to enroll patients and all study endpoints and additional analyses will be analyzed when enrollment has been completed. If an interim analysis is done, the significance level used for testing will be 0.0125. At the final analysis (if needed) the significance level used for testing will be 0.0194. These levels were derived using a power cumulative error spending function with the parameter (rho) set to 1.0. This setting produces Pocock type boundaries (i.e. approximately equal spending for the two tests).

If an interim analysis is not done, the final analysis will use a significance level of 0.025 for testing the primary endpoints.

SECONDARY ENDPOINTS

The secondary endpoints are safety related and examine the percentage of patients who receive safe and successful placement of the multipolar lead in the left and right phrenic nerve utilizing ultrasound guidance and the percentage of patients who experience one or more serious device/procedure-related adverse events during the study.

- The percentage of patients who receive safe and successful placement of the multipolar lead in the left and right phrenic nerve utilizing ultrasound guidance will be determined.
- Phrenic nerve stimulation in synchrony with Mechanical Ventilation (MV) breaths will be measured to verify that it occurs with inspiration.
- The percentage of patients who experience one or more serious device/procedure-related adverse events during the study will be reported.

	PEPNS Study Statistical Analysis Plan	Document Number SAP0001	Rev. Level 1
<small>CONFIDENTIAL: THIS DOCUMENT AND ALL INFORMATION CONTAINED HEREIN IS PROPRIETARY TO STIMDIA MEDICAL, INC. AND IS NOT TO BE DISCLOSED WITHOUT THE EXPRESS WRITTEN PERMISSION OF STIMDIA MEDICAL, INC.</small>			

Safe and Successful Lead Placement

The percentage of patients who received safe and successful placement of the multipolar lead on the Left and right phrenic nerve utilizing ultrasound guidance will be evaluated in terms of the mean and standard deviation for preparation, placement, securement, removal and twitching. Twitching includes neck spasms, arm movement, shoulder movement on unwanted visible stimulation. This will be reviewed on a site basis, by neck circumference and BMI.

Adverse Events

The percentage of patients who experience one or more serious device/procedure-related adverse events during the study will be reported. The evaluation results for the follow-up x-ray will also be noted.

Stim and Vent Synchrony

The phrenic nerve stimulation in synchrony with Mechanical Ventilation (MV) breaths will be measured to verify that it occurs with inspiration over all of the stimulated breaths for each of the patients. The synchrony on the detection of inspiration and expiration will be compared against the user set trigger flow section and compared to a fast trigger time which has been reported as 88 msecs.

Related Evaluations

Critical Care Pain Observation Tool (CPOT) assessments are made on all patients enrolled and will be reported before during and after stimulation on all patients. The pain assessment tool, CPOT, is based on four domains: the patient's facial expressions, body movements, compliance with ventilator (or voice use for non-intubated patients), and muscle tension. Each domain has a possible score of 0 to 2. The total score can vary between 0 and 8, where 0 indicates no pain behavior and 8 indicates clear signs of pain behavior.

Richmond Agitation and Sedation Scale (RASS) scores will be reported on all patients. The RASS measures agitation and sedation level, the score ranging from +4 to -5, where a score of 0 indicates an awake and adequate patient. Scores from -1 to -5 indicate an increasingly sedated patient, and scores from +1 to +4 indicate an increasingly irritable and agitated patient.

The CPOT and RASS scores will be evaluated to determine that the stimulation does not cause pain to the patient.

An assessment will be made to determine the sensitivity of the lead to patient position. Patient will be repositioned every 2 to 4hrs per hospital protocol and disease diagnosis requirements. Leads will be disconnected from the electrical stimulator using the extension lead during these non-stim periods. Reestablishing stimulation after reconnection will be evaluated along with the ability of the system to handle patient repositioning.

Vitals signs and blood gasses will be evaluated to determine if electrical stimulation does not have an untoward effect on patient. This will be evaluated by an expert in ICU ventilation / blood gas analysis.

ECG (electrocardiogram) will be reviewed before during and after electrical stimulation to ensure electrical stimulation is not adversely affecting the heart. This will be evaluated by an expert in the reading of ECGs.

	PEPNS Study Statistical Analysis Plan	Document Number SAP0001	Rev. Level 1
CONFIDENTIAL: THIS DOCUMENT AND ALL INFORMATION CONTAINED HEREIN IS PROPRIETARY TO STIMDIA MEDICAL, INC. AND IS NOT TO BE DISCLOSED WITHOUT THE EXPRESS WRITTEN PERMISSION OF STIMDIA MEDICAL, INC.			

Table 3: Patient Vitals and PEPNS Data

Patient ID	Age (yrs)	Weight (kg)	Height (cm)	Body Mass Index (BMI)	IV Line (Y/N)	ET / Trach (E/T)	Neck circumference at the cricoid cartilage (cm)	Screening Blood Pressure	PEPNS System Lead Preparation	PEPNS System Lead Placement	PEPNS System Lead Securement	Lead Removal/ Skin Closure Assessment	Twitching?	Follow-up X-Ray Normal?	Adverse Events?	Device Malfunctions?
P03S01																
P04S01																
P05S02																
P06S02																
P07S02																
P08S01																
P09S02																
P10S02																
P11S01																
P12S02																
Mean																
Stdev																

ADDITIONAL EVALUATIONS

Briefly state the overall scientific objectives of the analyses, including the key unanswered questions that these analyses are designed to address. If necessary, provide additional detail to formulate the objectives in statistical terms. Include a brief summary of how each objective will be addressed in the analyses.

The clinical effect of electrical stimulation will also be examined for the following:

- Time to weaning from mechanical ventilation data.
- Diaphragm thickness at 0, 24 and 48 hours.

The period of time each patient was on ventilation before electrical stimulation and the time to wean will be reported. The number of attempts to wean the patient before and after electrical stimulation will also be reported, if available.

The trend in diaphragm thickness increase/decrease for each patient and the aggregation of patients will be evaluated over time. The trend in diaphragm thickness based upon its initial thickness will also be evaluated. Correlations in diaphragm thickness increase and neck circumference will also be reviewed.

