6.3 Enrollment

Subjects will be screened to determine eligibility i.e., who meet all inclusion and exclusion criteria. Those subjects that meet the eligibility criteria and who agree to participate in the study will sign an Informed Consent form. Subject is deemed to be enrolled into study when the subject provides written informed consent and agrees to participate in the clinical investigation.

All patients that were attempted to be treated with the PEPNS System (i.e., intent-to-treat patients) but the procedure was aborted will also be followed for 30 days (+7 days) post index procedure for safety (i.e., adverse event collection).

A screening log will be used to determine why patients were screened out of the study.

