3. ANALYSIS SETS/ POPULATIONS/SUBGROUPS

The only analysis populations that will be analyzed in this SAP are per protocol population as the primary analysis and intent-to-treat population as the secondary analysis. No other populations will be statistically analyzed since it is too small a data set to assess other subgroups.

There will be summary tables created for patient demographics. In general, summary statistics will include the mean, median, standard deviation, minimum and maximum for continuous measures and the number and frequency for categorical measures. This summary data will be reviewed to see if there are any trends that may have impacted study endpoints.

	PEPNS Study Statistical Analysis Plan <small>CONFIDENTIAL: THIS DOCUMENT AND ALL INFORMATION CONTAINED HEREIN IS PROPRIETARY TO STIMDIA MEDICAL, INC. AND IS NOT TO BE DISCLOSED WITHOUT THE EXPRESS WRITTEN PERMISSION OF STIMDIA MEDICAL, INC.</small>	Document Number SAP0001	Rev. Level 1
---	--	-----------------------------------	------------------------

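### The SAP misquotes the protocol so that its intent-to-treat set holds aborted procedures only, and it lists no safety set for the first two patients

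*SAP*

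**What the plan says.** **ITT.** Protocol 6.3 (Enrollment) reads: "All patients that were attempted to be treated with the PEPNS System (i.e., intent-to-treat patients) but the procedure was aborted will also be followed", and goes on to set 30 days (+7) of safety follow-up. SAP section 2 says that the protocol defined ITT as "All patients that were attempted to be treated with the PEPNS System but the procedure was aborted". It then gives the set a role: "Primary and secondary endpoints for the study will be evaluated statistically in terms of per protocol (PP) and intent-to-treat (ITT) analysis". Per protocol (PP) is primary and ITT is secondary. Section 3 repeats that the only populations "are per protocol population as the primary analysis and intent-to-treat population as the secondary analysis", and does not redefine either.

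**First two patients.** SAP section 2 says of the two left-only patients: "Since these patients are stimulated on the left phrenic nerve only, they will be included for the safety analysis only". Section 3 adds: "No other populations will be statistically analyzed since it is too small a data set to assess other subgroups". Section 5 says that the PP primary analysis takes in all patients and all their data, as applicable. SAP Table 3 has a column for adverse events and columns for the lead-placement components. Its rows run from P03 to P12.

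**Endpoints affected.** Protocol 5.2 sets two per-patient percentages: safe and successful bilateral lead placement, and one or more serious device- or procedure-related events. For placement, the SAP's method is that it "will be evaluated in terms of the mean and standard deviation for preparation, placement, securement, removal and twitching".

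**Untreated subjects.** Protocol 14.4 bars from the analysis the data of subjects who did not receive PEPNS treatment.

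**The concern.** An ITT analysis beside a PP analysis is meant to show whether the result depends on leaving out patients in whom the procedure failed. A set made up of those patients alone cannot show this. It matters most for placement success, the endpoint that an aborted procedure affects most directly.

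The second matter is smaller. The first two patients were the first in humans, and later enrolment depended on their 30-day results. Whether they count in the serious-event percentage should be readable from the list of analysis sets, and it is not.

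**Working it through.** **1. The two sentences side by side.**

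| | Protocol 6.3 | SAP section 2 |
|---|---|---|
| Patients with attempted treatment | stated | stated |
| ITT label directly after that phrase | present | removed, with no ellipsis |
| Condition that the procedure was aborted | stated, after the label | stated |
| Main verb (follow-up for safety) | present | removed |
| Function | follow-up rule | definition of the ITT set |

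In the protocol the label most naturally attaches to attempted treatment, and the abort condition picks out who else is followed. In the SAP both conditions define the set: attempted and aborted. The protocol sentence is loose, but the quotation is altered on any reading of it.

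**2. Size of the ITT set as written.** Inputs: ten patients in Table 3, matching the nine men and one woman of SAP sections 7 and 8. The number of aborted procedures, *a*, is not in the documents. I assume *a* = 0, 1 or 2, in addition to the ten, and that all ten had both leads placed.

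| *a* | ITT as written | All bilateral attempts (10 + *a*) | Completed patients omitted by ITT as written |
|---|---|---|---|
| 0 | 0 | 10 | 10 |
| 1 | 1 | 11 | 10 |
| 2 | 2 | 12 | 10 |

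**3. Effect on placement success.** I assume that the *a* further attempts failed placement. Limits are exact (Clopper-Pearson) two-sided 95%: lower = Beta(0.025; x, n − x + 1), upper = Beta(0.975; x + 1, n − x), with lower 0 at x = 0 and upper 1 at x = n.

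| Basis | *a* = 1 | *a* = 2 |
|---|---|---|
| Table 3 patients | 10/10: 69.2% to 100% | 10/10: 69.2% to 100% |
| All bilateral attempts | 10/11 = 90.9%: 58.7% to 99.8% | 10/12 = 83.3%: 51.6% to 97.9% |
| ITT as written | 0/1: 0% to 97.5% | 0/2: 0% to 84.2% |

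**4. Effect on capture.** In the SAP model, "where subject is a random effect, and the outcome of capture is yes/no based on whether the stimulation captures the diaphragm". A set of zero or one patient gives no estimate of between-subject variance. SAP section 11 scores capture on each stimulated breath, so a patient whose procedure was aborted before stimulation adds no rows. A corrected ITT set therefore differs from PP on capture only if an abort followed some stimulation.

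**5. Serious-event denominator.** With no aborts beyond the ten, it is 10 without the first two patients and 10 + 2 = 12 with them. With no events, the upper limit is 1 − 0.025^(1/n):
- n = 10: 1 − 0.025^(1/10) = 30.8%
- n = 12: 1 − 0.025^(1/12) = 26.5%

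With one event, the estimate is 1/10 = 10.0% or 1/12 = 8.3%.

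**The case against.** The strongest reply is that the intent is clear. A statistician will read ITT as all attempted patients, the protocol's word order supports that, and the secondary endpoints carry no hypothesis test (protocol 6.9, SAP section 6). All this is fair and limits the effect. But the SAP gives an explicit contrary definition, attributes it to the protocol, and nowhere in the text available replaces it.

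Several stronger readings are tempting and do not hold:

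- *Placement success has no denominator at all.* Table 3 lists ten patients by ID against the same components that the method text names, and section 2 also runs the secondary endpoints on PP. What is missing is a denominator that counts failed attempts.
- *Some of the ten in Table 3 failed placement.* The documents report no abort. If the ten are the patients stimulated on both nerves, failed attempts would come on top of them.
- *The ITT capture analysis stops dead.* SAP section 2 allows another method if the model does not converge. That helps with a very small set, but it changes the method and not the membership, and an empty set stays empty.
- *The first two patients are shut out of the safety results.* Section 2 assigns them to the safety analysis and names adverse events, and the serious-event percentage covers the whole study. Including them is the natural reading. Section 3's restriction is on what is statistically analysed, and the reason it gives is subgroup size. What stands is an inconsistency: no such set is listed, section 5 puts all patients in PP, and Table 3 starts at P03.

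**Conclusion.** The ITT definition is wrong as written and should be corrected. The SAP's quotation does not match protocol 6.3, and the resulting set is either empty or made up only of aborted cases, so it cannot serve as the secondary analysis of any endpoint. The missing safety set is a real but smaller inconsistency, worth 30.8% against 26.5% on the upper limit with no events.

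The PP primary result is unchanged, and a corrected ITT set may add little on capture. The practical gain is in placement success: 10/11 or 10/12 on all bilateral attempts instead of 10/10, if one or two further attempts failed. Those figures rest on an assumed abort count and on the ten in Table 3 all having had both leads placed; neither is stated. The textual finding needs no such assumption.

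**What to change.** - **SAP sections 2 and 3, ITT:** define ITT as every patient in whom PEPNS treatment (lead insertion) was attempted, aborted or not. Quote protocol 6.3 in full or remove the quotation marks.
- **SAP sections 2 and 3, safety:** add a safety set of all patients with attempted insertion, including the first two, and use it for the serious-event percentage.
- **Placement success:** report a count and percentage over all attempted bilateral placements, with the two left-only patients shown separately.
- **Capture:** beside the ITT rate, give the number of attempted patients with no stimulated breath.
- **Consistency:** make SAP section 5 agree with section 2 on the first two patients. Reconcile the new sets with protocol 14.4 by stating whether attempted insertion counts as treatment.

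The cost is a few sentences in the SAP and perhaps a clarifying line in protocol 14.4. No new data are needed, because aborted patients are already followed for 30 days under protocol 6.3. The downside for the sponsor is that reported placement success may fall.
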